## LIST OF ABBREVIATIONS AND RELEVANT DEFINITIONS

ABR	ABR form, General Assessment and Registration form, is the application form that is required for submission to the accredited Ethics Committee (In Dutch, ABR = Algemene Beoordeling en Registratie)
AE	Adverse Event
AR	Adverse Reaction
CA	Competent Authority
CCMO	Central Committee on Research Involving Human Subjects; in Dutch: Centrale Commissie Mensgebonden Onderzoek
Conventional PET/CT	Where the term conventional PET/CT is used, we are referring to the conventional system that is used in this study: the Ingenuity TF PET/CT scanner (Philips Healthcare).
CT	Computed Tomography
ceCT	Contrast-enhanced CT scan, used for diagnostic purposes.
CV	Curriculum Vitae
Digital PET/CT	Where the term digital PET/CT is used, we are referring to the digital system that is used in this study: the Vereos PET/CT scanner (Philips Healthcare)
DSMB	Data Safety Monitoring Board
EU	European Union
FDG	Fluorodeoxyglucose
GCP	Good Clinical Practice
IB	Investigator's Brochure
IC	Informed Consent
IMP	Investigational Medicinal Product
IMPD	Investigational Medicinal Product Dossier
METC	Medical research ethics committee (MREC); in Dutch: medisch ethische toetsing commissie (METC)
MRI	Magnetic resonance imaging
NM	Nuclear Medicine
PA	Pathology results
PET	Positron Emission Tomography
(S)AE	(Serious) Adverse Event
Sponsor	The sponsor is the party that commissions the organization or

	performance of the research, for example a pharmaceutical company, academic hospital, scientific organization or investigator.
SUSAR	Suspected Unexpected Serious Adverse Reaction
TNM	TNM staging system; tumor (T), nodes (N) and metastasis (M)
Sv	The Sievert (Sv) is a derived unit of ionizing radiation, intended to represent the stochastic health risk. For radiation dose assessment, this is defined as the probability of cancer induction and genetic damage.
Wbp	Personal Data Protection Act (in Dutch: Wet Bescherming Persoonsgegevens)
WMO	Medical Research Involving Human Subjects Act (in Dutch: Wet Medisch-wetenschappelijk Onderzoek met Mensen)

## SUMMARY

**Rationale:** FDG-PET/CT imaging is important for staging, response monitoring and prognosis prediction in patients with cancer. However, the spatial resolution of current PET/CT systems is relatively low, limiting the detection of small lesions and accurate staging. In 2017, a new state-of-the-art digital PET/CT system will be installed at the NM department in Isala. It is expected that this new type of scanner contributes to more accurate staging and possibly more effective patient management. For a period of 6-12 months, both a conventional and a digital PET/CT system will be available in the NM department in Isala. This provides the unique possibility to evaluate the performance of the digital PET/CT system compared with conventional PET/CT. In this study, we will analyze the impact of digital PET/CT on the final diagnostic conclusion of the scan in patients with lung cancer, breast cancer and esophageal cancer.

**Objectives:** Primary objective: How does the diagnostic outcome of the digital PET/CT study compare to the outcome of conventional PET/CT in patients referred for (re)staging of lung cancer, breast cancer and esophageal cancer?

Secondary objective: What is the image quality (in both quantitative and qualitative terms) of digital PET as compared to conventional PET?

Both the primary and secondary objective are further specified in multiple detailed objectives.

**Study design:** Single center diagnostic accuracy study using intra-individual comparisons of PET/CT scans

**Study population:** 225 adults referred for a FDG-PET/CT scan in Isala to evaluate (suspected) lung cancer, breast cancer and esophageal cancer

**Main study parameters:** Primary: diagnostic outcome of the PET/CT study (number of detected lesions, TNM stage, clinical performance and accidental findings)

Secondary: image quality (rating image quality, diagnostic confidence, normal tissue appearance, lesion contrast and relation with EANM procedure guidelines)

**Nature and extent of the burden and risks associated with participation, benefit and group relatedness:**

- Additional scan time: Immediately after acquisition of the first PET/CT study, an additional PET/CT study will be obtained on the second system. The additional time for the second PET/CT scan will typically be 25 minutes (maximum 40 minutes), in which patients have to lie still on a scanner bed.
- Additional radiation dose: In a standard clinical FDG-PET/CT scan, the average dose is 14 milliSievert (mSv). This consists of the dose from a low-dose CT scan for attenuation-correction and the dose from FDG, depending on patients' body weight. The extra study-related low-dose CT scan will give an additional radiation dose of on average 6 mSv.

[figure not shown]
## **1. INTRODUCTION AND RATIONALE**

In 2013, more than 100.000 people were diagnosed with cancer in the Netherlands [1]. For an effective treatment, accurate staging of cancer is of great importance. In recent years, Positron Emission Tomography imaging combined with Computed Tomography (PET/CT) (Figure 1A) using the radioactive tracer  $^{18}\text{F}$ -fluorodeoxyglucose (FDG) became important for staging, response monitoring and prognosis prediction in patients with cancer [2-4].

With FDG-PET/CT, the glucose consumption of the human body is visualised. Most tumors and inflammations have an increased glucose consumption (thus increased FDG uptake) as compared to healthy tissue. Therefore, FDG-PET/CT is able to characterize malignancies and lesions, find metastases and determine the reaction to treatment by visualizing the degree of glucose (FDG) uptake which then shows up on a PET scan as a 'hotspot'. However, the spatial resolution of current PET/CT systems is relatively low. This results in an underestimation of the true FDG uptake of small lesions, which limits the detection of small lesions and accurate staging [5]. Improvements in PET detector technology may lead to improved image quality, which may translate into a more accurate diagnosis and ultimately may improve patient management.

Recently, a completely new type of PET detectors has been developed. After years of preparatory work, this new detector - called 'digital' detector - is now ready for incorporation into clinical PET/CT scanners. In 2017, one of these new types of PET/CT scanners (Figure 1B) will be installed in the Nuclear Medicine (NM) department in Isala, Zwolle, the Netherlands, as one of the first three systems in the world. As opposed to conventional scanners, this will be a digital system. The development of digital detectors for PET is expected to be a significant improvement in PET technology. PET scanners contain detector material in which a small light flash is produced when a photon strikes. In the old technology this small light flash was amplified using a photomultiplier. This is a glass vacuum tubes that finally yields a small electrical signal. The new digital PET scanner contain a silicon like counting device that allows direct digital photon counting of the flashes produced in the detector crystal, making the old-fashioned photomultiplier technique with its associated issues no longer necessary. This digital detector technology has the potential to improve PET imaging performance by providing better timing, energy and spatial resolution, higher count rate capabilities and linearity, increased contrast, reduced noise and lower required radiation dose. The CT gantry in this system is based on a commercially available CT that has not been modified in this device. This new type of PET scanner could potentially impact many clinical areas, including oncology, neurology and cardiology.

**Figure 1:** Pictures of a conventional (Fig. 1A) and a digital (Fig. 1B) PET/CT system.

The present study is intended to provide an initial assessment of the digital PET technology as used in a clinical setting. Patient images acquired on the digital PET system will be directly compared to images of the same patient acquired on a commercially released clinical PET/CT system equipped with the conventional photomultiplier tube detectors. For a period of 6-12 months, both a conventional and a digital PET/CT system are available in the NM department in Isala. In this period, extensive comparisons will be made between the conventional and novel digital type of PET/CT system. We will look at technical aspects such as image quality and lesion contrast, as well as clinical aspects such as the final diagnostic outcome of the study.

Furthermore, in the past few years procedure guidelines for FDG-PET tumor imaging were published by the European Association of Nuclear Medicine (EANM) to provide a minimum standard for the acquisition and interpretation of FDG-PET/CT scans [6]. These common standards are useful for quantification, valuable for response monitoring and increasingly used in multi-center trials. For the digital PET/CT system, acquisition- and reconstruction settings to fulfill these procedure guidelines yet need to be determined. Both calibration and validation of various system settings will be done in this study.

In the current study we will focus on three specific patients groups; patients with (suspected) lung cancer, breast cancer and esophageal cancer. There are multiple reasons for choosing these three patients groups for the present study:

1. FDG-PET/CT imaging is frequently used in these patient groups and has importance for diagnosis and disease staging.
2. In many cases within these groups, invasive staging procedures are performed in our hospital after PET/CT acquisition. This provides validation material that can be used to compare the clinical performance of conventional and digital PET/CT.

3. The disease incidence for these three cancer types is fairly high, providing the opportunity to reach a large enough study population within the selected period.
4. In these cancer types, the areas of nodal metastases are the mediastinum, the axillae and the upper abdomen. In this way we will obtain a fairly complete impression of PET staging properties in a large proportion of relevant tissue areas.

With the inclusion of these three patients groups, we will be able to make a comparison of conventional and digital PET/CT for these specified groups. However, we expect that such findings can be extrapolated to obtain an impression of the general clinical impact of digital PET/CT in all patients with cancer. Possibly the data from this study can be used to identify specific clinical areas where the digital technology may outperform conventional PET technology. Such initial data may be used to plan specific, hypothesis-driven follow-up studies to support performance and clinical claims for digital PET in general.

## 2. OBJECTIVES

### 2.1 Primary objectives: lesion detection properties

*How does the diagnostic outcome of the digital PET/CT study compare to the outcome of conventional PET/CT in patients referred for (re)staging of lung cancer, breast cancer and esophageal cancer? In other words: does digital PET detect more, the same or less abnormalities in patients with cancer.*

*More in detail:*

- 1.1 What is the difference in the number of lymph node metastases?
- 1.2 What is the difference in the number of involved lymph node stations?
- 1.3 What is the difference in the N status?
- 1.4 What is the difference in the number of distant metastases?
- 1.5 What is the difference in the number of involved distant metastatic systems (e.g. bone, brain, adrenals, liver, lungs)?
- 1.6 What is the difference in the M status?
- 1.7 What is the overall difference in final TNM classification?
- 1.8 Using a composite reference standard, what is the sensitivity, specificity and accuracy for lymph node staging, distant metastatic and overall staging of digital PET/CT as compared to conventional PET/CT?
- 1.9 Is there a difference in unrelated accidental findings?

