##### Sample size calculation for patients with lung cancer and patients with breast cancer:

###### **Objective 1.1 What is the difference in the number of lymph node metastases?**

*For power-calculations we translated this question into: does digital PET detect more, fewer or identical numbers of lymph node metastasis? We would like to be able to detect a 20% difference, if present. This level is generally considered relevant in obtaining a new type of scanner. Using the two-tailed sign-test, assuming a power of 80% and a p value of 0.05, this requires the inclusion of 49 subjects. After applying the 10%-correction for the inclusion of negative PET/CT scans, the number of required subjects is 54.*

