###### **Objective 1.3 What is the difference in the N status?**

*For power-calculations we translated this question into: is the N-status on digital PET equal, lower or higher as compared to conventional PET? We would like to be able to detect a 16% difference, if present. Using the two-tailed sign-test, assuming a power of 80% and a p value of 0.05, this requires the inclusion of 79 subjects. After applying the correction for negative PET/CT scans, the number of required subjects is 87.*

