#### 7.1.1 Primary objective: diagnostic outcome of the PET/CT studies

For each patient separately, the diagnostic outcome for the conventional and digital PET/CT study will be compared. Measured ordinal differences in for example the N-status or the TNM classification will be assessed based on two methods. The first method is based on the sign test, in which the comparison results in an agreement or a disagreement. The second method is based on the Wilcoxon signed-ranked test, in which the amount of disagreement is also taken into account. Moreover, we will calculate agreement percentages on the diagnostic outcome between both systems. Furthermore, using validation results as a reference, we will determine the sensitivity, specificity and accuracy for both NM physicians based on the following formulas:

$$\text{Sensitivity} = N_{PET \text{ positive}} / N_{\text{true positive}}$$

$$\text{Specificity} = N_{PET \text{ negative}} / N_{\text{true negative}}$$

$$\text{Accuracy} = (N_{PET \text{ positive}} + N_{PET \text{ negative}}) / (N_{\text{true positive}} + N_{\text{true negative}})$$

To test whether differences in sensitivity, specificity and accuracy between conventional and digital PET/CT are significant, we will apply the McNemar paired proportion test. A p value of less than 0.05 will be considered to indicate statistical significance.

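### Objectives 1.1 to 1.7 ask for the size and direction of the difference, but section 7.1.1 plans only sign and Wilcoxon tests and agreement percentages, with no paired difference and no confidence interval

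*Combined protocol and SAP*

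**What the plan says.** Section 2.1 frames the primary question partly by direction: whether digital PET finds more abnormalities, as many, or fewer. It then lists detailed objectives. Objectives 1.1 to 1.6 each ask what the difference is, as in "What is the difference in the number of lymph node metastases", and 1.7 asks for the overall difference in TNM classification.

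Section 4.4 recasts objective 1.1 for the power calculation as "does digital PET detect more, fewer or identical numbers of lymph node metastasis". It continues "We would like to be able to detect a 20% difference, if present" and says of the 20%: "This level is generally considered relevant in obtaining a new type of scanner". For lung and breast cancer it states "Using the two-tailed sign-test, assuming a power of 80% and a p value of 0.05, this requires the inclusion of 49 subjects". For objective 1.3 it states "We would like to be able to detect a 16% difference, if present" and, "assuming a power of 80% and a p value of 0.05, this requires the inclusion of 79 subjects". It does not call the 16% relevant, and no level is given for any other objective. The esophageal calculations use the same 20% and 16% with 65% power and p = 0.10, giving 28 and 42.

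Section 7.1 counts every disagreement as a difference. Section 7.1.1 plans the sign test, the Wilcoxon signed-rank test and, in addition, "we will calculate agreement percentages on the diagnostic outcome between both systems". For objective 1.8 it plans sensitivity, specificity and accuracy, compared by McNemar's test. The criterion is p < 0.05. No net difference, mean or median paired difference, or confidence interval appears for any primary objective, and no step compares a result with 20% or 16%.

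**The concern.** A p-value does not give the size of a difference, and an agreement percentage gives neither its size nor its direction. As written, section 7.1.1 does not commit the trial to any figure that answers objectives 1.1 to 1.7. The answer that the two scanners perform alike, which section 2.1 allows for, cannot be drawn from a non-significant test. It needs an interval narrow enough to exclude differences that matter.

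This matters for the intended uses. The introduction says the data may be used to plan hypothesis-driven follow-up studies, and section 9.6 says the results may support marketing and regulatory claims. Both need an effect size with its precision, on a scale fixed before the data are seen.

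**Working it through.** **Inputs.** From section 4.4: differences of 20% and 16%; 80% power at 0.05 (49 and 79 subjects); 65% power at 0.10 (28 and 42 subjects); 90 patients each with lung and breast cancer. The documents give no share of patients whose two scans agree, so all counts of discordant patients below are assumed for illustration.

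**1. Reproducing the plan's sample sizes.** Exact two-sided sign test among n patients whose scans differ. The null share higher on digital PET is 0.50 and the alternative is 0.50 + d. Reject at k or more (or n - k or fewer), with k the smallest value for which 2·P(X ≥ k | 0.50) ≤ α. Take the smallest n that reaches the power.

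| d | α | Power | n found | n stated | k | Power at n |
|---|---|---|---|---|---|---|
| 0.20 | 0.05 | 80% | 49 | 49 | 32 | 0.810 |
| 0.16 | 0.05 | 80% | 79 | 79 | 49 | 0.807 |
| 0.20 | 0.10 | 65% | 28 | 28 | 19 | 0.683 |
| 0.16 | 0.10 | 65% | 42 | 42 | 27 | 0.660 |

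All four match. Reading 20% as 60:40 instead gives, by Noether's formula, (1.960 + 0.842)² / (4 × 0.10²) ≈ 197. The plan's 20% and 16% are therefore 70:30 and 66:34 splits among discordant patients, which section 4.4 does not say.

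**2. What agreement leaves open.** Let b patients be higher and c lower on digital PET, out of 90. Net share = (b - c)/90; SE = √(b + c - (b - c)²/90)/90; 95% CI = net ± 1.96·SE. For 16:4, net = 12/90 = 0.133 and SE = √(20 - 1.6)/90 = 0.0477.

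| b : c | Agreement | Sign test p | Net share (95% CI) |
|---|---|---|---|
| 16 : 4 | 77.8% | 0.012 | +13.3% (4.0 to 22.7) |
| 10 : 10 | 77.8% | 1.00 | 0% (-9.7 to 9.7) |
| 4 : 16 | 77.8% | 0.012 | -13.3% (-22.7 to -4.0) |

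One agreement figure fits all three, and the two-sided p-value is the same for the first and third.

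**3. Non-significance is not equality.** For 40:26, p = 0.109 and net = 14/90 = 15.6%. SE = √(66 - 196/90)/90 = 0.0888, so the CI is -1.8% to 33.0%. The test is not significant, but a net change of a third of patients is not excluded.

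**4. Significance is not the planned effect.** With 49 discordant patients, significance starts at 32/49 = 65.3% (p = 0.044; Clopper-Pearson 95% CI 50.4% to 78.3%). That is below 70%, and the interval reaches almost to 50%.

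**5. The two scales are not interchangeable.** A 70:30 split is a net 40% of discordant patients. As a share of all patients it is 0.40 × (discordant/all), so it moves with the tie rate. In 90 patients, 34:15 (about 70:30) is 19/90 = 21.1%, while 63:27 is 36/90 = 40%.

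**6. Test and interval can conflict.** For 30:16 of 90, the exact sign test gives p = 0.054, but Tango's score interval for the net share is 0.8% to 29.6% and excludes zero. At zero that interval corresponds to the asymptotic McNemar test: z = 14/√46 = 2.06, p = 0.039.

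**The case against.** The best defence is that the question is partly directional. Section 2.1 says so, section 4.4 translates 1.1 and 1.3 that way, and the sign and Wilcoxon tests address direction. The Wilcoxon test also uses the amount of disagreement. The study calls itself an initial assessment, and anyone running a sign test will have the higher and lower counts in hand. This stands in part: direction is a legitimate half of the question. But no shift estimate accompanies the Wilcoxon test, the counts are not named as a result, and a study meant to inform later studies has more need of estimates, not less.

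Three stronger readings are tempting, and the documents do not support them.

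- A reader might infer that the plan yields nothing but p-values. It also yields agreement percentages and, for 1.8, point estimates of sensitivity, specificity and accuracy.
- A reader might infer that the planned test favours small differences over large ones. In 90 patients, 6:0 gives p = 0.031 at a net 6.7%, while 40:26 gives p = 0.109 at a net 15.6%. That ranking holds only for the net share of all patients. On the scale behind the plan's sample sizes it reverses: 6:0 is 100% of discordant patients, 24:10 is 70.6%, 30:16 is 65.2% and 40:26 is 60.6%.
- A reader might infer that net-share intervals should be judged against 20% or 16%. Those figures belong to the discordant-pair scale, only the 20% for 1.1 is called relevant, and neither is set as a margin that an interval must clear.

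**Conclusion.** The concern holds in a limited form, as a change that should be made. Sections 2.1 and 7.1.1 do not match: objectives 1.1 to 1.7 ask for size as well as direction, and the planned outputs fix neither. Objective 1.8 lacks only intervals and a stated paired difference.

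In the illustration, a single agreement figure of 77.8% is compatible with net changes from -13.3% to +13.3%. The width of that range depends on assumed discordant counts. The gap itself does not, since agreement has no direction whenever some patients differ. The scale of the 20% and 16% rests on exact reproduction of all four sample sizes under one reading; the documents do not state it. Nothing here shows that the tests are invalid or that the sample size must change.

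**What to change.** In section 7.1.1, per tumour group:

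- For each of 1.1 to 1.7, report the numbers of patients higher, equal and lower on digital PET, and the net share of all patients with a 95% CI for paired proportions. State the denominator (section 4.4 expects about 10% negative scans) and how the two physicians' readings enter.
- For the count objectives (1.1, 1.2, 1.4, 1.5), add the mean paired difference with a patient-level bootstrap CI.
- For 1.8, give the paired differences in sensitivity, specificity and accuracy with CIs.
- Keep the tests as support, and name a test and an interval that match: Tango's interval with the asymptotic McNemar test, or the exact sign test with a Clopper-Pearson interval for the share higher among discordant patients.

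In section 4.4, state that the 20% and 16% are 70:30 and 66:34 splits among patients whose scans differ. Compare results with these levels only on that scale, using the share higher among discordant patients with its CI. Treat only the 20% for 1.1 as a level called relevant. The 16% for 1.3 is a detectable difference, and the other objectives have no level.

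The cost is SAP wording, minor programming and a longer results table. No new data or patients are needed.

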### 2.2 Secondary objectives: image quality

*What is the image quality (in both quantitative and qualitative terms) of digital PET as compared to conventional PET?*

- 2.1 How do experienced readers rate digital PET image quality?
- 2.2 How does digital PET influence diagnostic confidence for N- and M-staging?
- 2.3 Are there differences in the appearance of normal tissues between digital and conventional PET?
- 2.4 What is the lesion detectability for digital PET as compared to conventional PET?
- 2.5 What is the optimal cut-off value of tumor uptake or lesion contrast to distinguish between benign and malignant lesions for digital PET, and how does this compare to conventional PET?
- 2.6 What are the optimal settings for digital PET to fulfill EANM procedure guidelines?
- 2.7 Do conventional and digital PET/CT studies, that both fulfill EANM procedure guidelines, provide comparable final PET/CT results?

Both the set of primary and secondary objective research questions can be studied in a variety of subgroups, based on tumor type, lesion size or other clinical factors.

